### Table of Study Procedures (3/4)

Phase III Study, Group 3 (Russian Federation): 7 or 8 Visits, 5 Vaccination Visits, 5 Telephone Calls, 3 Blood Samples, 11 Months Duration per Subject for Subjects Randomized to Receive MenACYW Conjugate Vaccine

Visit / Telephone Call	V0	V01	TC1*	V02	TC2*	V03	V04	TC3*	V05	TC4†	V06	TC5*	V07
Approximate Subject Age	2 months‡	2 months	-	3 months	-	4.5 months	6 months	-	7 months	-	12 months	-	13 months
Trial timeline (days, months)		Day 0 + 1 day	V01 +8 days	V01 +30 days	V02 +8 days	V02 +45 days	V03 +45 days	V04 +8 days	V04 +30 days	V06 -14 days	V05 +5 months	V06 +8 days	V06 +30 days
Time windows (days)	NA	+4 days	+2 days	+14 days	+2 days	+14 days	+14 days	+2 days	+14 days	+2 days	+14 days	+2 days	+14 days
Informed consent form signed and dated	X	X											
Inclusion / exclusion criteria	X	X											
Collection of demographic data	X	X											
Medical history§	X	X											
Urine Sample, (8 mL)**	X												X
Physical examination & temperature	X	X††		X‡‡		X‡‡	X‡‡				X‡‡		
Review of temporary contraindications for Blood Sampling (BL)§§***	X								X				X

Visit / Telephone Call	V0	V01	TC1*	V02	TC2*	V03	V04	TC3*	V05	TC4†	V06	TC5*	V07
Approximate Subject Age	2 months‡	2 months	-	3 months	-	4.5 months	6 months	-	7 months	-	12 months	-	13 months
BL	BL0001 6 mL†††								BL0002 6 mL‡‡‡				BL0003 6 mL†††
Review of warnings and precautions and / or contraindications to vaccinations		X		X		X	X				X		
Review conditions for withdrawal§§§		X		X		X	X				X		
Contact IRT system for randomization / allocation of subject number / vaccine assignment		X											
Contact IRT system for vaccine dose number for all vaccines to be given				X		X	X				X		
Vaccination with MenACYW conjugate vaccine				X			X				X		
ENGERIX B®*****††††† vaccination							X						
Prevnar 13® vaccination†††††		X				X							
Pentaxim® vaccination†††††				X		X	X						
MMR vaccination†††††											X		

Visit / Telephone Call	V0	V01	TC1*	V02	TC2*	V03	V04	TC3*	V05	TC4†	V06	TC5*	V07
Approximate Subject Age	2 months‡	2 months	-	3 months	-	4.5 months	6 months	-	7 months	-	12 months	-	13 months
Immediate surveillance (30 minutes)		X		X		X	X				X		
Telephone Call			X		X			X		X		X	
Diary Card (DC):													
Provided		DC1		DC2		DC3	DC4		DC5		DC6		
Reviewed				DC1		DC2	DC3		DC4		DC5		DC6
Collected				DC1		DC2	DC3		DC4		DC5		DC6
Collection of reportable medications	To be reported throughout the study period												
Recording of solicited injection-site and systemic reactions		X		X		X	X				X		
Recording of unsolicited AEs	Collected from D0 to D30 after each vaccination visit												
Reporting of SAEs / AESIs‡‡‡‡	To be reported throughout the study period												
Trial Termination													X

Abbreviations: V: Visit; TC: telephone call; D: Day; IRT: interactive response technology; AE: adverse event; SAE: serious adverse event; AESI: adverse event of special interest

\*This call is made 8 days after the respective vaccinations. If Day 8 falls on a weekend or holiday, the telephone call may be made on the following business day. During this telephone call, the staff will find out whether the subject experienced any SAEs (including AESIs) not yet reported and will remind the subject's parent/guardian to continue using the diary card, to bring the diary card to the study center at the next visit, and confirm the date and time of the next visit

†This call is made 14 days before V06 to remind the subject's parent(s) of the forthcoming visit. If the subject's participation is discontinued due to withdrawal of parental / guardian consent or for other reasons, the staff will check over the phone to see if the subject received any medications or treatments or experienced any SAEs (including AESIs) that have not yet been reported to the study personnel and will make arrangements to retrieve the diary card.

‡"2 months" means from the 2nd month after birth to the day before the 3rd month after birth (2 months to 2 months 29 days).

§ Medical history to include history of maternal immunization against tetanus.

\*\* The results of urine laboratory tests, performed for the subject in terms of routine practice, can be used, if the tests were done within 7 days before Visit 0. In this case, no urine sample will be collected at Visit 0.

†† Physical examination to be performed as per routine standard of care. Temperature needs to be measured before each vaccination and recorded in the source documents.

‡‡ Physical examination should be performed on the basis of relevant medical history at the time of the visit, according to the investigator's clinical judgment. Temperature needs to be measured before each vaccination and recorded in the source documents. As a reminder, a temperature  $\geq 37.0^{\circ}\text{C}$  in the Russian Federation is a temporary contraindication. The vaccine should not be administered until the condition has resolved or the febrile event has subsided.

§§ Should a subject receive oral or injectable antibiotic therapy within 3 days prior to the second blood draw, the investigator will postpone that blood draw until it has been 3 days since the subject last received oral or injectable antibiotic therapy. Postponement must still be within the timeframe for blood draw. If postponement would result in the sample collection falling outside of this timeframe, the blood sample should be collected without postponement, and it should be documented appropriately that the sample was taken less than 3 days after stopping antibiotic treatment.

\*\*\* If vaccines are to be administered at the same visit, blood sample will be drawn prior to vaccinations.

††† The results of CBC and biochemistry laboratory tests, performed for the subject in terms of routine practice, can be used, if the tests were done within 7 days before Visit 0 and Visit 7. In this case, the blood sample volume collected at Visit 0 and Visit 7 will be 4 mL.

‡‡‡ The minimal blood volume required for study immunogenicity objectives is 4 mL at Visit 0 and Visit 7 and 6 mL at Visit 5.

§§§ Conditions for withdrawal are listed in [Section 5.2.8](#) of the protocol.

\*\*\*\* In the event ENGERIX B® cannot be supplied in the Russian Federation, a locally licensed monovalent hepatitis B vaccine will be administered instead. Further details will be provided in the CSR.

†††† Routine vaccines should be administered in accordance with official recommendations in the Russian Federation. In the event M-M-R®II combination vaccine cannot be supplied or is unavailable in the Russian Federation, locally licensed MMR or MM+R vaccines will be administered instead. Further details will be provided in the CSR.

‡‡‡‡ AESIs will be collected throughout the trial, as SAEs, to ensure that the events are communicated to the Sponsor in an expedited manner and followed up until the end of the follow-up period or resolution, as per the assigned causality.

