#### *The Russian Federation*

- Group 3: MenACYW conjugate vaccine at 3, 6, and 12 months of age + routine pediatric vaccines at 2, 3, 4.5, 6, and 12 months of age
- Group 4: Routine pediatric vaccines at 2, 3, 4.5, 6, and 12 months of age

All subjects in Groups 1 and 2 will receive either MenACYW conjugate vaccine or Menveo® concomitantly with the following routine pediatric vaccines in accordance with available official recommendations *in Mexico*:

- Prevnar 13® (pneumococcal 13-valent conjugate vaccine [PCV13]) at 2, 4, 6, and 12 months of age\*
- Hexacima® (DTaP-IPV-HB-Hib) at 2, 4, 6, and 12 months of age
- RotaTeq® (pentavalent rotavirus vaccine [RV5]) 2, 4, and 6 months of age
- MMR (measles, mumps, rubella [MMR] vaccine) at 12 months of age

All subjects in Group 3 will receive MenACYW conjugate vaccine concomitantly with the following routine pediatric vaccines; and all subjects in Group 4 will receive the following routine pediatric vaccines alone in accordance with the National Immunization Calendar (NIC) recommendations in *the Russian Federation*:

- Prevnar 13® (pneumococcal 13-valent conjugate vaccine [PCV13]) at 2 and 4.5 months of age\*
- Pentaxim® (DTaP-Hib-IPV) at 3, 4.5, and 6 months of age†
- ENGERIX-B® (hepatitis B vaccine) at 6 months of age‡
- MMR vaccine at 12 months of age§

\* No immunogenicity endpoints will be measured for this vaccine in the Russian Federation. The PCV13 routine vaccine recommended at 15 months of age in the Russian Federation is considered as out of scope for this study and will not be provided by the Sponsor but procured by the sites as per their standard practices.

† The 4th dose of Pentaxim®, which is administered at 18 months of age, is considered out of the scope of the study, and it will not be provided by the Sponsor but procured by the sites as per their standard practices. Subjects will be instructed to receive it for completion of the Pentavalent series as per the NIC of the Russian Federation.

‡ In the event ENGERIX B® cannot be supplied in the Russian Federation, a locally licensed monovalent hepatitis B vaccine will be administered instead. Further details will be provided in the CSR.

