### **Note about Screening / Enrollment Visits**

Visit 0 = Screening visit for subjects in the Russian Federation only.

In the Russian Federation, Visit 0 and Visit 1 may take place on the same day, or Visit 1 may take place up to 5 days after Visit 0.

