***The Russian Federation***

Visit 0: Inclusion, Allocation of Subject's number, Urinalysis, and Blood Sampling:

- 1) Give the subject's parent(s) information about the trial, answer any questions, obtain written informed consent in duplicate (in 2 originals) and give the parent(s) 1 signed original as per local regulations and practicea.
- 2) Check inclusion and exclusion criteria for eligibility.
- 3) Collect demographic data.
- 4) Obtain verbal medical history about the subject, including ongoing medications and history of maternal immunization against tetanus.
- 5) Perform a physical examination, including but not limited to examination of the head (including ear, nose, and throat), neck, thorax (including heart and lungs), abdomen, and extremities. If a routine examination, CBC, biochemistry, and urinalysis laboratory tests, had been performed within the last 7 days before Visit 0 by the Investigator, a sub-Investigator, or a licensed practitioner; it does not need to be repeated unless the Investigator considers it is necessary to repeat.
- 6) Take the subject's temperature by the axillary route.
- 7) Contact the IRT system for randomization /allocation of subject number / vaccine assignment.

---

a In the Russian Federation, as per local regulations, only the subject's parent(s) are entitled to sign an ICF. A child under the responsibility of a guardian will not be included in the study.

The signature of only 1 of the parents will be required on the ICF.

- 8) Obtain the first 6 mL blood samplea (see [Section 7.1](#) for detailed instructions regarding the handling of blood samples). If attempts to obtain the first blood draw are unsuccessful (after attempts as per local regulations / practice), then Visit 0 can be rescheduled to a later date at which point inclusion reasonable /exclusion criteria must be re-validated. If the first blood draw cannot be obtained, the subject will be withdrawn from the study without being vaccinated.
- 9) Obtain a urine sample (approximately 8 mL).b
- 10) Collect reportable concomitant medications information.
- 11) Complete relevant source documentation and CRF pages for the visit.
- 12) Confirm subject's eligibility based on the results of the baseline testing of CBC, blood chemistry, and urinalysis.

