**Note:** If Visit 1 (the vaccination visit) is performed on the same day as Visit 0, only the procedures from step number 4 onwards in the Study Procedures listed under Visit 1 below are to be followed.

Visit 1 (1 [+4] days after Visit D0): Randomization, Inclusion, and Vaccination

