***Steps 5 through 10 for all subjects***

Visit 1 (1 [+4] days after Visit Day 0): Inclusion, Blood Sampling (BL), and Vaccination:

- 4) Review warnings and precautions to vaccinations.
- 5) Review contraindications to vaccination
- 6) Contact the IRT system for randomization / allocation of subject number / vaccine assignment
- 7) Administer the appropriate study vaccines per Operating Guidelines. Each vaccine should be administered in an assigned location and documented appropriatelyc.

---

a The results of CBC and biochemistry laboratory tests, performed for the subject in terms of routine practice, can be used, if the tests were done within 7 days before Visit 0. In this case, the blood sample volume collected at Visit 0 will be 4 mL.

b The results of urine laboratory tests, performed for the subject in terms of routine practice, can be used if the tests were done within 7 days before Visit 0. In this case, no urine sample will be collected at Visit 0.

c Failure to administer vaccines in the designated limb will not constitute a protocol deviation, but should be recorded as a comment in the CRF. If the initial vaccines are administered in the wrong limbs, this should be corrected for subsequent injections.

- **Groups 3 and 4:** Prevnar 13®: inject IM into the anterolateral area of the thigh (preferably the left thigh)a
- 8) Keep the subject under observation for 30 minutes and record any AE in the source document.
  - 9) Give the parent a diary card (DC1), a thermometer, and a ruler, and go over the instructions for their use.
  - 10) Remind the parent to expect a telephone call 8 days after Visit 1 and to bring back the diary card when they return for Visit 2 at a specified date and time.
  - 11) Remind the parent to notify the site in case of an SAE.
  - 12) Complete the relevant CRFs for this visit.

Telephone Call 1 (8 [+2] days after Visit 1)

**Note:** If Day 8 falls on a weekend or a holiday, the telephone call may be made on the following business day.

- 1) Record relevant information concerning the subject's health status on the telephone contact form. If an SAE has occurred that has not yet been reported, follow the instructions in [Section 10](#) for reporting it.
- 2) Remind the parent to do the following:
  - Complete the D0 to D07 pages of the diary card.
  - Complete the remaining pages of the diary card, and bring them to the next visit.

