## 6.4 Blinding and Code-breaking Procedures

This trial is open-label; therefore, there is no need for code-breaking procedures. Until database lock and to prevent biases, the laboratory personnel performing the serology testing will be blinded to the group assignment. The laboratory will have a written procedure detailing how the blinding will be maintained.

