## 6.5 Randomization and Allocation Procedures

On the day of enrollment, subjects who meet the inclusion/exclusion criteria and whose parent / guardian signs the ICF will be randomly assigned in a 2:1 ratio in Mexico, and in a 2:1 ratio in the Russian Federation such that Group 1 will have 200 subjects, Group 2 will have 100 subjects, Group 3 will have 150 subjects, and Group 4 will have 75 subjects.

Site staff will connect to the IRT system, enter the identification and security information, and confirm a minimal amount of data in response to IRT-system prompts. The IRT system will then provide the vaccine assignment and subject number. The full detailed procedures for Group allocation are described in the Operating Guidelines. If a subject who has enrolled is not eligible to participate in the study, then the subject's information will only be recorded on the subject-recruitment log.

Subject numbers that are assigned by the IRT system will consist of a 12-digit string (a 3-digit country identifier, a 4-digit study center identifier, and a 5-digit subject identifier). For example, Subject 840000100005 is the fifth subject enrolled in Center Number 1 in the US (840 being the US country code).

Subject numbers should not be reassigned for any reason. The randomization codes will be kept securely in the IRT system.

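### In Russia the open-label arm is assigned at Visit 1, 30 to 44 days before Groups 3 and 4 differ, so early losses and Visit 1 safety reports can occur with the arm known

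*Protocol*

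**What the plan says.** Protocol Tables of Study Procedures (3/4) and (4/4) mark "Contact IRT system for randomization / allocation of subject number / vaccine assignment" under V01 only, and SAP Tables 3.5 and 3.6 repeat the row. In Protocol 5.1.4 (Russian Federation) the Visit 1 heading reads "Visit 1 (1 [+4] days after Visit D0): Randomization, Inclusion, and Vaccination", and step 6 of that visit is the same IRT contact.

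The same section also lists "Contact the IRT system for randomization /allocation of subject number / vaccine assignment" as step 7 of Visit 0. That is ahead of the first blood draw (step 8) and of the confirmation of eligibility from laboratory results (step 12). The Visit 0 heading itself speaks only of allocating a subject number. The note on screening in 5.1.1 adds that "Visit 1 may take place up to 5 days after Visit 0". Section 6.5 does not settle which visit is meant: "On the day of enrollment, subjects who meet the inclusion/exclusion criteria and whose parent / guardian signs the ICF will be randomly assigned". It goes on to say that the IRT gives the site the vaccine assignment together with the subject number.

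Table 5.2 shows what is given. At V01 both groups receive Prevnar 13 only. At V02 Group 3 receives MenACYW plus Pentaxim and Group 4 receives Pentaxim alone.

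On masking, 6.4 states "This trial is open-label; therefore, there is no need for code-breaking procedures"; only the serology laboratory is kept blind. Section 5.1.2 justifies the open label by differences between the meningococcal vaccines in schedule, appearance and preparation. No text explains why Russian children are allocated before any meningococcal vaccine is due.

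**The concern.** In an open-label trial, knowledge of the arm can influence who stays, who is vaccinated on time and what is reported. That is unavoidable once the arms diverge. Here it is accepted for a month or more beforehand, at a visit where the group makes no difference to what is given. A subject number and a Prevnar 13 dose number are all that Visit 1 needs.

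Three things can therefore happen with the arm known: withdrawal between Visits 1 and 2, contraindication and postponement decisions at Visit 2, and safety reporting after Visit 1. The comparison exposed is Group 3 versus Group 4, for safety and for responses to the routine vaccines. Group 4 (n=75) is the trial's only arm without any meningococcal vaccine, and 5.1.2 calls the assessment of interference with routine vaccines crucial. Each child lost from Group 4 is 1/75 = 1.3% of it.

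**Working it through.** **1. The plan's own figures.** Protocol 12.5 and SAP 5.5 give a probability of about 95% of seeing an AE at least once. With P = 1 - (1 - p)^n:
- n=525, p=0.57%: 0.9503
- n=350, p=0.85%: 0.9496
- n=200, p=1.5%: 0.9513
- n=150, p=2%: 0.9517

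All four reproduce and are not in dispute. The n=350 cohort (200 + 150) counts every Group 3 child as exposed to MenACYW.

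**2. Interval with the arm known before it matters.** V02 is V01 + 30 days with a +14 day window, so 30 to 30 + 14 = 44 days. If Visit 0 step 7 is followed instead, the maximum is 5 + 30 + 14 = 49 days.

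**3. What is recorded in that interval.** Solicited reactions cover D0-D7. Unsolicited AEs run to D30 (procedure tables) or to the next visit (5.1.3, collection of safety data).

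**4. Where a child who leaves before V02 ends up.**
- FAS1 (12.2.1; SAP 5.2.2) needs one infant dose and a valid infant post-vaccination serology result. Without the 7-month sample the child is out.
- PPAS1 (12.2.4; SAP 5.2.1.1) needs the completed schedule and an in-window sample. The child is out. A child whose V02 dose is postponed past the window is also out.
- SafAS2, SafAS4, SafAS5 and SafAS6 need vaccination at the later visits. The child is out.
- SafAS1 and the any-dose SafAS (12.2.2; SAP 5.2.3) keep the child. Any-dose safety is grouped by the vaccine received at the first dose, which in Russia is Prevnar 13 in both groups. A Group 3 child who leaves early is then either counted in Group 3 without having received MenACYW or cannot be told apart from Group 4.

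**5. Size.** No loss rate is given, so these are assumptions.
- Loss of 1%, 3% or 5% of 225: 2.25, 6.75 or 11.25, that is, about 2 to 11 children.
- Common loss of 1%, 2%, 5% or 10% leaves 148.5, 147, 142.5 or 135 of 150 in Group 3 receiving MenACYW. P(at least one AE at 2%) is then 0.950, 0.949, 0.944 or 0.935.
- For the MenACYW cohort, the same range takes 350 down to 348.5-335 and P(at least one AE at 0.85%) from 0.950 to 0.949-0.943.
- Differential loss (Group 3 versus Group 4) changes the 2:1 ratio at V02. For 0% v 5%, 150/71.25 = 2.11; for 2% v 10%, 147/67.5 = 2.18; for 5% v 0%, 142.5/75 = 1.90; for 10% v 2%, 135/73.5 = 1.84.

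**6. How much of the infant follow-up this is.** From V01 to the V05 sample is 30 + 45 + 45 + 30 = 150 days, up to 150 + 4 x 14 = 206 with windows. The interval before V02 is 30/150 = 20% to 44/206 = 21% of that.

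**The case against.** The strongest reply is that the consequence is small. Every analysis is descriptive, no Group 3 versus Group 4 hypothesis is tested, serology is read blind, and the Russian primary objective describes Group 3 alone. The loss rates are assumed and nothing shows that they would differ by arm. The loss of precision is slight. All of this stands, and it limits the point to a modest one.

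Several stronger readings are tempting but not supported:
- A reader might infer that Group 4 is the only control without MenACYW. Group 2 receives Menveo, so Group 4 is only the sole arm with no meningococcal vaccine.
- A reader might infer that FAS1 demands the later doses. It asks for one infant dose plus serology; early leavers drop out for want of the sample.
- A reader might infer that reactions are reported for the full 30 to 44 days. Solicited reactions stop at D7; only unsolicited AEs run on.
- A reader might infer that parents are told the arm at Visit 1. The protocol says that the IRT informs the site and leaves allocation details to the Operating Guidelines, which are not available. Parental knowledge is probable under an open label, but it is an inference.
- A reader might infer that post-MenACYW safety tables are contaminated. The per-visit safety sets already exclude children who never reach V02.
- A reader might infer that later allocation would remove arm-aware selection. It removes the first fifth of the time to the 7-month sample; knowledge of the arm continues from V02 onward.

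What the reply does not supply is a reason for allocating early. The stated grounds for the open label explain why Group 3 cannot be masked from V02, not why the arm is disclosed at a visit with no meningococcal vaccine.

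**Conclusion.** The point holds in limited form. The Russian arm is assigned and given to the site 30 to 44 days (up to 49 on the Visit 0 text) before it changes anything, with no stated rationale. Early losses, Visit 2 vaccination decisions and Visit 1 safety reports can therefore be influenced by the arm. The effect is confined to descriptive Group 3 versus Group 4 comparisons; the primary endpoint involves no such comparison.

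The size rests on an assumed 1-5% loss before V02 (about 2-11 of 225 children) and on the inference that parents learn the arm. The documents give no evidence of differential loss. The case for change rests on the avoidable exposure and the low cost rather than on a demonstrated bias. The conflict between Visit 0 step 7 and the procedure tables needs reconciling in any event.

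**What to change.** At V01 keep only the subject number and the Prevnar 13 dose number. Randomise at V02, at the IRT contact already listed there as step 5, which follows the review of warnings, contraindications and withdrawal conditions (steps 2-4). Equivalently, let the IRT hold the assignment and release it only at that contact. Align Section 6.5, Visit 0 step 7, the Visit 1 heading and step 6, the Group 3 and Group 4 procedure tables, and SAP Tables 3.5 and 3.6. Mexico stays as it is, because its arms differ from Visit 1.

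In the safety analysis, show Russian Visit 1 data by the arm later assigned. Summarise children who leave before V02 separately and do not count them as MenACYW recipients. This needs small wording changes to SafAS1 and the any-dose SafAS.

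For children already allocated under the present text, the reporting part can still be applied: tabulate losses between V01 and V02 by randomised group, and read Russian SafAS1 as a check, since a Group 3 versus Group 4 difference there cannot be an effect of MenACYW.

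The cost is an IRT setting and wording. If 225 are enrolled and randomisation is moved to V02, slightly fewer than 225 are randomised, since 5.2.8 does not replace withdrawn children. Randomising a full 225 would need 225/(1 - d) enrolled: 228, 230, 237 or 250 for an assumed loss d of 1%, 2%, 5% or 10%. No dose or visit changes, and the number treated in each arm does not fall.
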